2 STUDY SUMMARY

Background: Hemiplegic Cerebral Palsy (HCP) causes lifelong weakness and stiffness of one side of the body, impacting everyday functioning. Most affected children do not have access to effective intensive upper limb therapy.

Aim: To determine whether a wrist-worn device and software (including a smartphone application), incorporating positive feedback and peer support, can encourage increased use of the affected arm and hand during everyday activities.

Study design: Proof of concept study

Methods:

Participants: 20 children aged 8-18 years with HCP, their age-matched controls ("Buddies"), therapists and family members. The children with HCP will be recruited by clinicians at Newcastle upon Tyne Hospitals Trust and at the Evelina London Children's Hospital and through local self-help groups. The children will each nominate and approach their potential "buddy", who will then decide with their family whether they wish to learn more about the study and contact the research team if this is the case.

Intervention: Baseline (2 weeks): the device records arm activity without giving feedback. Active feedback (6 weeks): the device records and gives feedback (through the app) as well as personalised prompts during the day based on encouraging arm activity if this falls below a pre-set personalised threshold. Final (2 week) period: as for baseline.

Assessment:

At the start of the study the children will take part in a range of standardised hand and arm assessments conducted by an experienced occupational therapist. This will include the Assisting Hand Assessment (AHA) or equivalent Ad-AHA (age 13 years+), the Tyneside Pegboard Test (manual dexterity) and the ABILHAND-Kids questionnaire. Proof of concept assessment will be quantitative, produced by the data collected from the accelerometer with regards to the level of arm activity. In addition, there will be a qualitative component, via weekly meeting by phone/Skype/face to face. This will help to understand the acceptability and feasibility of implementation of the device and help with troubleshooting.

Analysis: We will assess feasibility and, through discussion with families, "Buddies" and therapists, acceptability. Hand function will be assessed at baseline. Changes in arm activity (derived from accelerometer data in the devices) will be analysed using single case experimental design for proof of concept that the approach can increase use of the affected upper limb.

4 BACKGROUND

Background: Hemiplegic Cerebral Palsy (HCP) affects around 39 000 people in the UK. HCP causes weakness and stiffness of one side of the body, impacting on activities of daily living [1, 2], peer relationships [3], quality of life and self-esteem [4], with long-term consequences for independent living and employment [5, 6]. Intensive therapy interventions improve upper limb function in children with HCP compared with usual (low-frequency, low-intensity) care [7], Intensive interventions require high levels of resources (e.g. 1:1 staffing levels, 8 hours/day in 2-week blocks) and are unavailable to most children. Approaches such as constraint therapy (in which the less-affected arm is restrained) are somewhat intrusive, and still require intensive therapy to promote use of the affected arm [8-10]. Fitting therapy around the home and school routine is challenging and requires motivation, patience and understanding: children with HCP require more practice than their typically developing peers to learn motor tasks [11]. It is hard to achieve adequate practice throughout the day without "nagging".

Use of wearable technology to monitor activity levels [12] has the potential for marked behaviour change [13, 14]. Smartphone apps promoting self-monitoring and self-management are becoming popular for young people with chronic health problems e.g. diabetes and epilepsy [15, 16]. Through a collaboration between the Institute of Neuroscience and Open Lab (both at Newcastle University), funded by the Stroke Association, wrist-worn devices, and a software interface for providing feedback on use of the affected arm, were developed for adults with hemiplegia. The device contained an accelerometer to monitor arm activity;

it also reminded them to use the affected arm by vibrating discreetly if activity during the previous hour fell below a personalised, agreed threshold [17]. In a pilot trial there was a 16% increase in arm activity (counts per minute) in the hour after a prompt, compared with the preceding hour.

This approach is a promising real-world solution for children with HCP, empowering them to take control of their own improvements using technology with which they are familiar and comfortable. Children are comfortable with the use of smartphone applications, and therefore in this project they receive feedback through a smartphone app rather than a software interface on a personal computer. The app provides feedback and motivation. We will also collect normative data from a "Buddy" for each young person with HCP, to capture the variation in activity (and between limbs) in typically developing peers in the same settings.

5 AIMS

- 1) To test the feasibility and acceptability of a smartphone application and wrist-worn devices for children with HCP, providing performance-related feedback to reinforce and reward activity of the affected upper limb in everyday life.
- 2) To assess proof of concept that this approach can increase activity of the affected upper limb.

6 METHODS

6.1 Design: Proof of concept mixed methods study

6.1.1 Inclusion Criteria

A) Children/young people with HCP who are:

1) 8-18 years old

2) Manual Ability Classification (MACS) level I-III. MACS is a 5-point classification scheme for the children's ability to handle objects. Those at MACS IV-V struggle significantly more to undertake daily activities independently, which would affect the use of the wrist-worn device and the smartphone [18].
3) Fully informed signed parental consent and assent from parents

B) Typically developing controls:

Each of the children/young people will select a "buddy" who is a typically developing peer (sibling/school friend) within the same age range 8-18 years, (same age or in the same school year) who will act as a control to collect a comparative/normative dataset. These children/young people will have normal hand function. Again, fully informed consent (parental for children)/assent (child) will be obtained.

C) Therapists of children with HCP:

Following consent from the parents of the children/young people with HCP, we will ask their therapists to take part in providing feedback. These will be either physiotherapists or occupational therapists and are eligible if they are providing input related to upper limb function.

For all of the above, adequate command of the English language and fully informed consent (and for children, assent).

6.1.2 Exclusion Criteria

A) Registered blind or partially sighted, as they will not be able to see the visual (LED) cues or app feedback.

- B) Unable to detect vibratory cues to wrist from the device.
- C) Significant cognitive and/or language deficit precluding ability to use the device and application.
- D) Current involvement in another research study likely to interfere with the conduct of this study.

6.1.3 Sample Size

20 children/young people with HCP and a "buddy" (typically developing) for each child will participate in the study. This sample size is expected to be sufficient for qualitative data saturation [19], permitting a range of scenarios in regards to demographics (across two sites) and functional ability to illustrate proof of concept. We will also recruit the therapists of the children/young people with HCP. The quantitative analysis will be on a single case experimental design basis.

6.1.4 Intervention

All children/young people taking part in the study will wear a device on each wrist, containing an accelerometer and sending data through Bluetooth linking to a smartphone application which can derive information on the activity of each arm. The devices are similar to a Fitbit and are CE tested activity trackers.

The children/young people will also borrow a smartphone for the course of the study if they do not already have one. If they do have a smartphone which is of adequate specification, the app will be downloaded on to their smartphone.

We will make sure the children/young people and families are provided with information/education about safe internet use as part of the project. Currently available suitable sources of information include the Safer Internet Centre (www.saferinternet.org.uk/advice-centre/young-people/resources-11-19s) which has suitable resources; and the Online Safety Guide from Internet Matters: https://www.internetmatters.org/advice/online-safety-guide.

The children/young people and families will be provided with instructions regarding the use of the app and phone, as well as on charging the devices. These instructions will be finalised at the end of the current development phase of the research. We will check that they understand the instructions and can carry them out. We will also provide them with contact details in case they have any questions or difficulties.

The children/young people will wear the wristbands all day each day for the 10 week period, one on each wrist. They will be removed at night, and for charging, and for activities which might be detrimental to the devices such as swimming, washing etc.

During the first 2 weeks, the devices will record arm activity but will not provide any hourly prompts to move. There will also not be any personalised feedback through the app. The aim of the first 2 weeks is to obtain baseline data on activity levels for each young person.

Personalised thresholds for activity levels will then be set, based on this baseline data and after negotiation with the children/young people and families. In a previous study in adults with hemiplegia, most chose to aim for a 10% increase in activity of the affected arm with respect to baseline. For those without hemiplegia, the prompts will be simply based on baseline data.

Activity levels will by necessity vary during the day and be different for school days and weekends. However, the ratio of the activity of the affected versus unaffected arm provides a method of modulating the prompts in a responsive manner for those with hemiplegia.

During the next 6 weeks, the personalised thresholds will be used to set prompts (visual and/or vibratory cues) through the wristbands for the children/young people to use their arm and hand if activity falls below the set threshold. It will be possible for a researcher to adjust the thresholds for prompts, through a webbased login, if necessary.

At the end of the day the children/young people will be encouraged to view the app to gain information regarding how much they managed to improve the activity of the affected arm. To provide motivation, this improvement will also be translated into reward points to use in a simple game they can play on the app.

During the final 2 weeks of the study the children/young people will not be given prompts or feedback: this will allow us to see if the increased level of activity can be maintained without this information.

The children/young people and families will have weekly contact with a member of the research team over the phone, via Skype or if needed face to face to troubleshoot and obtain feedback.

6.1.5 Control Group: Buddies

The role of the "buddies" is to obtain normative data to compare to each of the young people with HCP, and to capture the variation in the level of activity and between limbs in typically developing peers within the same situation, throughout a similar day. Buddies will therefore also wear the two wristbands and have access to the app for a 10 week period.

6.1.6 Assessments and Outcome Measures

The children/young people will take part in assessments at baseline to test upper limb function, undertaken by an occupational therapist. Children/young people will wear the wrist-worn devices during the assessments – this will allow us to obtain additional data regarding movements, pairing video data, accelerometry data and comparing with the clinical scores. During the assessments, the accelerometers will be set to sample at high frequency (e.g. 100 Hz) to capture the movement data at high resolution. The devices are lightweight (similar to Fitbits) and will not interfere with performance.

6.1.6.2 Manual Ability Classification System (MACS) [18] - children with UCP only

MACS is a validated 5 point classification system describing how those with CP use their hands in everyday activities. MACS I represents the highest level of self-initiated hand use. Parents, or the children/young people themselves, can complete the assessment by following the simple questions on the flow chart. The MACS is stable over time.

6.1.6.2 Assisting Hand Assessment (AHA) or equivalent Adolescent-AHA (age 13y+) – children with UCP only [20, 21]

AHA is a standardised evaluation of hand and arm baseline function. It is a measure of how efficiently people who suffer from conditions such as HCP spontaneously use their affected arm and hand in bimanual tasks. The children/young people will take part in a semi-structured 'play' session that uses a specific testing kit of toys and lasts 10 to 15 minutes. This session is recorded and reviewed based upon 22 items. Each of these items relates to a different action during the test: these actions are rated on a 4-point scale with higher scores representing better function. The AHA test is valid for children between the ages of 2 years to 12 years old. The test is fully validated and has excellent psychometric properties. There is an equivalent adolescent-AHA (Ad-AHA) for children ages 13-18 years. Ad-AHA was developed due to those over the age of 12 finding the AHA 'play session' unappealing due to its 'childish' nature. The raw scores for these assessments are converted through Rasch analysis to a '0-100 unit' logit-based AHA score. The Ad-AHA can

be scored exactly as the AHA: the two assessments can be considered as equivalent. We will collect this data from all children and young people taking part, to gather baseline information about arm movements.

6.1.6.3 ABILHAND-Kids Questionnaire - children with UCP only [22]

The ABILHAND-Kids questionnaire is used to gauge manual ability whilst performing daily tasks. The questionnaire is completed by the parents (taking around 5 minutes) and is based upon their perception of their child's manual ability (regardless of which hand is used). The assessment has been validated and is suitable for children aged 6-15 years. Each item is rated on a 3-point scale as to whether the child would find that task impossible, difficult or easy. The questionnaire scoring system is Rasch-based and is completed online. For those aged 16 and over, the ABILHAND questionnaire will be used instead.

6.1.6.4 Question regarding Cognitive Performance at School – all children/young people

We will ask parents about their child's performance at school, and if they require(d) additional support.

6.1.6.5 Accelerometry Data – all children/young people

The children/young people with HCP and their buddies will be wearing wrist-worn devices on both of their wrists during the day to collect data regarding arm movements, for a period of 10 weeks. Accelerometers within these devices provide information in relation to the arm activity that they perform during this period. The data over the 10-week period will be exported with 1-minute resolution, except for specified periods e.g. during specific assessments, during which higher resolution (e.g. 100 Hz) data will be collected. This data will allow calculation of the signal vector magnitude for each arm, and a comparison of each, over time.

6.1.6.7 Tyneside pegboard test – all children/young people [23]

This assessment was developed at Newcastle, to assess and compare unimanual and bimanual function. The pegboards are adapted to be accessible by people with conditions such as HCP. The assessment can be completed in around 15 minutes and simply involves removing and replacing pegs from a board.

6.1.6.7 Qualitative Study – all families

Throughout the study the children/young people and their buddies (and parents of both as appropriate) will take part in a weekly overview with a member of the research team. This will be done via phone/Skype or if needed face to face to gather information on acceptability of the device and the app as well as to undertake any troubleshooting. The families will be asked about the effect of using the device on social contact, activities and participation, and if the children suffer from any discomfort/fatigue (which is unlikely). The children/young people will be able to comment on any difference the device has made to their lives and if they think that the device has had a perceived effect on their ability to concentrate on other tasks (e.g. lessons). The sessions will be audio recorded and transcribed (anonymised) prior to subsequent analysis (see below).

6.1.6.8 Information on healthcare resource use

This will be collected initially before the study starts and will be reviewed during the weekly discussions throughout the study. This will concern if the child/young person has seen their occupational/physiotherapist and if so, the nature of any input/advice.

6.1.6.9 Information from therapists

Telephone interviews with therapists undertaken at the end of the limb movement data collection period will explore their views on the approach.

6.2 Study Conduct

6.2.1 Approach to participants

Children/young people with HCP who are eligible to take part in the study will be identified by clinicians at the Newcastle upon Tyne Hospitals NHS Foundation Trust, and by clinicians at the Evelina Children's Hospital in London. These children/young people will then be referred through their regional clinics once a member of the team has had a discussion with them and their families about the research project. We will also advertise the project through local self-help groups for families with children/young people with hemiplegia (former HemiHelp groups) in the Newcastle and London regions.

Once these children/young people have been referred, the families and children/young people will be given more information about the study and will be provided with an information sheet. An age-appropriate information sheet will be given. They will then be given time to go away and consider their participation in the study and at any point will be able to ask a member of the team any questions they might have. If the children/young people and their parents decide they want to take part, they will be asked to identify a potential "buddy" to take part too. They will be given a flyer to provide to the buddy and family, who will be encouraged to get in touch and provide their contact details so that they can discuss the study in detail with a researcher. They can then decide whether they wish to take part. Likewise, the families of the young people will contact any physiotherapist or occupational therapist who is providing input regarding upper limb function, so that they can also be approached regarding their decision to take part in the study.

The children/young people with HCP, their families and their buddy and their families will be made aware that they are free to drop out of the study at any time even after signing a consent form, without having to provide a reason.

6.2.2 Recruitment and Consent

The families will have adequate time since being initially approached about the study to consider if they wish to take part. They will be able to contact one of the research team and if they do want to continue they will be able to attend a meeting so that we can go through the information sheet with them to ensure that they fully understand the study and to answer any further questions. They will be informed that if they decide to not take part in the study that their children and their clinical care will not be adversely affected in any way.

Parents will sign consent forms on behalf of their children, who will also provide assent. Those aged 16 years and over will provide their own consent.

Therapists will provide written informed consent to be approached for telephone interviews (providing the parents of children with hemiplegia consent for the therapists to be approached).

The researcher providing the children with information will have experience with research involving minors so that they can assess whether they think that the child has fully understood and that they have enough information to make an informed decision.

6.2.3 Action in event of poor recruitment rate

We will monitor the rate of recruitment between the Newcastle upon Tyne Hospitals Foundation Trust and the Evelina Children's Hospital. We will raise awareness of the study at both sites through local talks. If the level of recruitment remains low we may consider involving other sites/PICS.

6.2.4 Schedule of assessments

6.2.4.1 Children/young people with hemiplegia

		Baseline function data collection		Active feedback period							Final recording period	
Assessment	Baseline	1W	2W	3W	4W	5W	6W	7W	8W	9W	10W	
Manual Ability Classification System (MACS)	X											
Assisting Hand Assessment (AHA)/ Adolescence-AHA	x											
ABILHAND-Kids (or ABILHAND if aged 16 years and over)	X											
Ask about school inc. performance/support at school	x											
Accelerometry Data (from wristworn devices)	X	x	x	x	x	x	x	x	x	x	x	
Tyneside Pegboard Test	X											
Telephone interviews		x	x	X	x	x	x	x	x	X	x	

6.2.4.2 Typically developing buddies

Assessment	Baseline	1W	2W	3W	4W	5W	6W	7W	8W	9W	10W
Manual Ability Classification System (MACS)											
Assisting Hand Assessment (AHA)/ Adolescence-AHA	x										
ABILHAND-Kids											
Ask about school incl. performance/support	X										
Accelerometry Data	X		x	x	x	x	x	x	x	x	x
Tyneside Pegboard Test	X										
Telephone interviews		x		x	×	×	x	×	x	x	x

6.2.5 Digital Recordings

The data recorded by the accelerometer will be stored and used for analysis. In addition the therapist interviews will be audio recorded so analysis can be conducted at a later date, as will telephone interviews with families. These interviews will be sent for transcription to UK based services with strict data privacy policies, which comply with GDPR; and who have ISO 27001 certification. This data will be stored on a secure server at Newcastle University, which only members of the Limb Buddies research team will be able to access. This activity data will be coded via a study ID and assessment number: no names of participants will be used though pseudonyms will be used in the telephone transcripts.

Videoed assessments will be labelled by study number (not name), and transferred electronically using Newcastle University File Transfer system to a secure server at Newcastle University, downloaded and anonymised prior to analysis of limb movement in relation to limb accelerometry data. Anonymisation will be done using Adobe Premier Pro video editing software (or similar) to blur out faces and any other identifying information.

6.2.6 Data analysis

Qualitative data: Analysis of the telephone interviews throughout the study will provide a large dataset in regards to the acceptability and the feasibility of the device and the app during the children's everyday life. The qualitative analysis will be conducted according to the standard procedures [24] including open and focused coding, constant comparisons and memoing [25], deviant case analysis [26], and mapping [27]. When analysing this data we will specifically explore the issue in regard to age and gender on the acceptability of the device/app, ease of use, fidelity and the perceived benefits of use.

Quantitative data: The data recorded from the accelerometer will be analysed to see if the prompts to increase arm activity were effective. The change in arm activity will be measured by a signal vector magnitude of overall arm movement for pre-specified periods of time including the hour before a prompt and the hour following a prompt. This data once analysed can be further categorised in terms of the level of arm use (e.g. if movements are light, moderate or vigorous) in comparison to the child's baseline threshold.

The level of change in arm activity is judged from the extent to which baseline measures do not overlap with those in the intervention phase (percentage of non-overlapping date) [28]. From the data collected from each of the participants a 10% increase in the relative arm use in the active monitoring period compared with baseline function will be considered a proof of principle that the approach can increase arm use in daily activities.

In addition to this the relationship between baseline AHA/Ad-AHA, ABILHAND-Kids and Tyneside Pegboard test scores and improvement in arm use will be explored.

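### The before/after-prompt comparison picks its before hour for being low, so the triggering measure rises on average even if prompts do nothing

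*Protocol*

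**What the plan says.** Section 6.2.6 states the purpose: the accelerometer data "will be analysed to see if the prompts to increase arm activity were effective". It measures change as signal vector magnitude over "pre-specified periods of time including the hour before a prompt and the hour following a prompt". It names no reference set of low hours without a prompt.

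Section 6.1.4 gives the trigger: the wristbands cue children "to use their arm and hand if activity falls below the set threshold". It describes the first two weeks as a time when "the devices will record arm activity but will not provide any hourly prompts to move", so prompts appear to work on an hourly cycle. The Background gives an explicit trigger window, but only for the adult precursor device, which worked by "vibrating discreetly if activity during the previous hour fell below a personalised, agreed threshold". Section 6.1.4 also says that the ratio of affected to unaffected arm activity offers a way to modulate prompts in children with hemiplegia, and that a researcher can adjust thresholds.

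Section 6.2.6 has two further assessments, both at phase level: non-overlap of baseline and intervention data, and a 10% increase in relative arm use in the active period against baseline.

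**The concern.** An hour enters the comparison as a before hour because it was low. The following hour is not selected in that way. Unless hourly activity is perfectly autocorrelated, the following hour lies closer to the child's usual level on average, whatever the prompt does. This is regression to the mean produced by the prompt rule.

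The before/after comparison is the only named analysis that is specific to prompts. If its raw result is reported, an inert prompt can look effective, and a useful one will look more effective than it is. The adult pilot result in the Background, a "16% increase in arm activity (counts per minute) in the hour after a prompt, compared with the preceding hour", is a comparison of the same type and has the same weakness.

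**Working it through.** **Inputs from the protocol.** Trigger: activity below a personal threshold (6.1.4). Windows: the hour before and the hour after a prompt (6.2.6). Threshold: set from baseline data and negotiated; in the adult study "most chose to aim for a 10% increase in activity of the affected arm with respect to baseline" (6.1.4). No hourly SD, autocorrelation, alpha or power is given for this comparison. The pilot's 16% therefore cannot be reproduced.

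**Assumptions.** Hourly CV, lag-1 autocorrelation ρ, and threshold c as a multiple of the baseline mean, shown as ranges. The true prompt effect is zero unless stated.

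**Closed form (normal hourly activity, mean 1, trigger and outcome the same measure).**

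- a = (c − 1)/CV
- before = 1 − CV·φ(a)/Φ(a)
- after = 1 + ρ(before − 1)
- apparent rise = after/before − 1

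With c = 1.0, CV = 0.3, ρ = 0.5: a = 0; before = 1 − 0.3 × 0.3989/0.5 = 0.7606; after = 1 − 0.5 × 0.2394 = 0.8803; rise = 0.8803/0.7606 − 1 = 15.7%.

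With c = 1.1 and the same CV and ρ: a = 0.333; before = 1 − 0.3 × 0.3774/0.6306 = 0.8205; after = 0.9102; rise = 10.9%.

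The rise vanishes only at ρ = 1.

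**Simulation (log-normal AR(1), 12 waking hours, 40,000 days, zero effect, same measure).**

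| Threshold | CV | ρ = 0 | ρ = 0.5 | ρ = 0.7 |
|---|---|---|---|---|
| 100% of mean | 30% | 26% | 13% | 8% |
| 100% of mean | 50% | 46% | 23% | 14% |
| 110% of mean | 30% | 20% | 10% | 6% |

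**Ratio as trigger (zero effect, CV 30%, ρ = 0.5, threshold ratio 1, between-arm correlation 0.5 to 0.9).** The false rise goes from about 7% down to 3% for the affected arm and from about 15% down to 6% for the ratio. It is about 0% for both arms combined.

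**Does an unprompted reference repair it? (CV 30%, ρ = 0.5, threshold at the mean.)** Apply the same rule to hours without cues, and call those that qualify virtual prompts.

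- No effect: real and virtual prompts both show 13.2%, so the contrast is 0.
- True 10% effect, all prompts: 20.0% raw against 13.2%; 1.200/1.132 − 1 = 6.0%. This is too small, because an earlier prompt in a run has already raised a later before hour.
- True 10% effect, first prompt of each run: 22.0% against 10.7%; 1.220/1.107 − 1 = 10.2%. The effect is recovered.
- No prompt effect, but feedback and rewards lift active-phase activity by 10%: the contrast still shows a false rise of about 4 percentage points (about 8 at ρ = 0). The threshold is fixed while the whole level has moved.

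**The case against.** The strongest reply is that this comparison does not decide the study. Aim 2 concerns the approach as a whole, and the proof-of-principle rules in 6.2.6 compare phases and do not select low hours. The before/after comparison carries no test or success threshold, and the study has 20 children with a sample size justified by qualitative saturation. All of this stands. A reader might infer that the 10% criterion is also invalid; the protocol does not support that. Those rules, however, cover prompts, feedback and rewards together and cannot show whether the prompts worked.

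Second, the previous-hour trigger is explicit only for the adult device, and a ratio trigger with total activity as outcome gives almost no false rise. This also stands, and it is why the size is given as a range.

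Third, 6.2.6 says that the periods include these hours, so others may be used, and an SAP not seen here may add a reference. That is possible. But the protocol itself names the comparison and its purpose, so this is more than an omitted detail.

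Three further inferences go too far:

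- That the summed change over a run of consecutive prompts must be positive. This needs a fixed threshold on the outcome measure itself, and 6.1.4 allows ratio modulation and threshold changes.
- That hours with the device off trigger prompts. No section says so.
- That the pilot's 16% is an artefact or miscalibrates this study. It lies within the range possible with no effect, but the protocol does not use it to size or calibrate anything.

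**Conclusion.** The point holds for the prompt-specific comparison. The upward bias in the triggering measure follows from the trigger rule in 6.1.4 and the windows in 6.2.6, and needs only that hourly activity is not perfectly autocorrelated. Its size rests on assumptions about CV, autocorrelation, threshold and trigger that the protocol cannot confirm: about 6–46% when trigger and outcome coincide, and much less, down to about zero for both arms combined, when the arm ratio is the trigger. The phase-level conclusion is not affected by this selection. As written, the raw before/after change cannot show that prompts were effective.

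**What to change.** Amend the quantitative part of section 6.2.6 as follows.

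- State which measure and window trigger a prompt, so that 6.1.4 and the analysis can be read together.
- Apply each child's prompt rule to the unprompted two-week baseline to mark virtual prompts. Report the before-to-after change at real prompts relative to that at virtual prompts.
- Use worn hours only, and match on hour of day and on school or non-school day.
- Use only the first prompt of each run, with standard errors clustered by child. Clustering does not replace the first-prompt restriction: it corrects precision, not the dilution shown above.
- Use the final two weeks only as a sensitivity reference. They exist to test whether increased activity persists, so they are not neutral.
- State that a general rise from feedback or rewards can leave residual bias (about 4 percentage points for a 10% lift at CV 30%, autocorrelation 0.5).
- Do not present the raw before/after rise as evidence that prompts work.

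The cost is wording and some programming; the one-minute baseline data are already to be collected. Fewer prompts will be analysed, and the reported prompt effect will be smaller than the raw one.
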